Description of Decision Making Process: This 10-item measure asks parents and adolescents in the UC Group only to report how often they did certain activities during the decision making process and how it affected their choice, the outcome of the decision making process and how satisfied they are with their decision. This measure was constructed for this study to enable participants randomized to the UCP group to describe the process by which they made a decision about CSII or CGM. If decision making has been actively deferred, that will be treated as a decision having been made. If decision making has simply not occurred, in the absence of a definite statement to defer decision making until some point in the future, this measure will be obtained at Visits 3 and 5. Information yielded from this measure will be used primarily for descriptive purposes to enable readers to place the UCP condition in a concrete perspective.

Measures obtained at Visit 3 and Visit 5

Decision Regret Scale (DRS): The DRS is a 5-item scale for measuring a patient's degree of regret (or satisfaction) after a specific decision.¹⁶³ Items are rated on a 5-point scale ranging from "strongly agree" to "strongly disagree", and higher scores reflect more perceived regret. Internal consistency was .81 in a prior study. The scale will be completed by parents and adolescents in both the SMDM and UCP groups. Administration time is about 2-3 minutes.

SURE Test: The SURE Test is a 4-item screening tool to measure decisional conflict in patients facing clinical decisions in primary care. If the total score is less than 4, the patient is experiencing decisional conflict. The SURE Test will be completed by parents and youth in both groups at Visit 3 and at Visit 5. Administration time is about 2-3 minutes.

Measure obtained at Baseline (Visit 1) and Visit 2

Test of CSII or CGM Knowledge: Each parent and adolescent will complete a 5-item test of CSII or CGM knowledge based on content of the respective decision aids at baseline and at Visit 2 (Or the first visit after the

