Diabetes Self Management Profile-Self-Report form: The DSMP-SR was derived from the previously validated DSMP structured interview.¹⁶⁴⁻¹⁶⁵ The 24-item DSMP-SR with separate youth (age > 11) and parent forms quantifies treatment adherence and was validated recently.¹⁶⁵ Mean + SD DSMP total scores (maximum possible = 84) were $54.7 + 12.6$ for 145 parents and $54.5 + 12.3$ for 129 adolescents with mean HbA_{1c} of 8.7%. Internal consistency was .82 for youths and .80 for parents. Youth-parent scores correlated .64. Correlation with HbA_{1c} was .46 for parents and .37 for youths. Administration time is 10 minutes. Consideration will be given to forming a parent-adolescent composite score for this measure if their scores correlate > 0.70 at any measurement point Decision Aid Utilization Tracking (SMDM participants only) A benefit of developing the decision aids for delivery via a web platform relative to hard copy decision aids is that utilization tracking can be achieved automatically to record and date/time stamp virtually every keystroke made by a decision aid user. While far more data elements could be extracted from the back-end of the web platform, in consultation with E-City Interactive, we have selected these specific data elements as ones we will routinely track. E-City Interactive will prepare a monthly report format and regularly provide the research team with these statistics both in aggregate and within individual study participants:

- Total number of users
- Total number of users that logged in at least once
- Number of site visits per user with date and time
- User path through whole site
- User path through educational content only
- Amount of time each user spent on each page
- Quiz answers
- Quiz answers changed per user
- Quiz answers shared per user
- Content engagement (# of slides viewed per content page, amount of video viewed per content page)
- Decision slider location
- Decision slider movement and site page where movement took place
- Direction of decision slider movement
- Number of times the decision slider was moved per user
- Engagement with content feedback widget and corresponding content page
- Total number of times each piece of content was visited
- Number of times content was bookmarked

B.4. Measurement Schedule*

	Visits (~Months)				
	V1 (0)	V2 (3)	V3 (6)	V4 (9)	V5 (12)
General Information Form (P)					

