Demographic and baseline characteristics (age, race, ethnicity, family composition, marital status, SES), primary and secondary end points, and biochemical, psychological, and behavioral variables will be summarized by intervention groups. One way analysis of variance (ANOVA) of each continuous baseline characteristic and a Fisher exact test/chi-square test/CMH test for each categorical variable will be used to compare the intervention groups at baseline. These comparisons will be used to evaluate the balance of demographic and baseline characteristics among intervention groups. Analyses of primary and secondary end points will be adjusted for significantly imbalanced baseline characteristics. For those measures completed separately by parents and youths, when parent and youth scores are correlated at $r > .70$, a combined parent-adolescent score for that variable will enter analyses. Otherwise, separate analyses will be completed on parent and adolescent scores. A mixed models (or multilevel modeling) approach will be used to test the hypotheses listed below.¹⁶⁹⁻¹⁷² The methods advocated by Holmbeck¹⁷³ will be used to evaluate baseline variables that moderate/predict SMDM-UCP treatment effects on primary study outcomes. Candidate moderator variables will include SES, youth age and gender, race/ethnicity, family structure, and health literacy and numeracy. The methods advocated by Holmbeck¹⁷³ will also be used to evaluate variables that may mediate SMDM-UCP treatment effects on primary study outcomes. In each case, these will include measures that are obtained serially and concurrently with the primary study endpoints. SAS subroutines for addressing the potential confounding influences of time- dependent covariates (e.g. youth age) will be employed as needed in these mediational analyses. With five measurement points for HbA_{1c} and hypoglycemia, the proposed mixed models approach will be capable of detecting longitudinal associations among study variables that are non-linear in form.

Hypothesis 1: Compared to UCP, the SMDM group will have significantly more favorable status in terms of indices of optimal use of CSII or CGM, scores on the CSII or CGM Knowledge Test, SURE Test, Decision Regret Scale, Diabetes Technology Questionnaire and SMDM Satisfaction Scale at each follow-up measurement point.

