Hypothesis 2: Compared to UCP, the SMDM group will have significantly more favorable status in terms of scores for treatment adherence (DSMP-SR), HbA_{1c}, and frequency of moderately severe or severe hypoglycemia at each follow-up measurement point.

Hypothesis 3: Effects of SMDM on indices of optimal use of, and satisfaction with, CSII or CGM will be mediated by changes in the measures of decision quality (Test of CSII or CGM Knowledge, Decision RegretScale, SURE Test, Decision Satisfaction Scale).

Hypothesis 4: Significant moderators of benefit from SMDM along the measured outcomes will include baseline measures of socioeconomic status, health literacy and numeracy, youth age, and family structure.

Hypothesis 5: SMDM will have indistinguishable beneficial effects on the primary study outcomes regardless of which clinical decision (CSII or CGM) was the focus of the SMDM intervention.

Statistical Power Statistical power to detect treatment effects of interest on the primary endpoints was assessed using the online DSS Research Statistical Power Calculator.¹⁷⁴ With enrollment of 166 eligible youth and parents and attrition of 10% over the 12-month study, and a resulting “Completer” sample size of 150, the study will have statistical power of .87 to detect a moderate treatment effect of ~0.4 SD on the measures of decision quality and CSII or CGM optimal use. Even though statistical power remains adequate for detection of somewhat smaller treatment effects, effects of less magnitude are unlikely to have sufficient clinical significance to warrant the added cost and inconvenience of implementing SMDM.

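### The Hypothesis 3 mediation models have no planned adjustment for time-fixed common causes of decision quality and device outcomes, so the indirect effect is biased by an amount the plan cannot bound

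*Combined protocol and SAP*

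**What the plan says.** Hypothesis 3 (section B.5) reads: "Effects of SMDM on indices of optimal use of, and satisfaction with, CSII or CGM will be mediated by changes". The mediators it lists, as indicators of decision quality, are the Knowledge Test, Decision Regret Scale, SURE Test and a decision satisfaction scale.

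The data management and analysis text in B.5 makes two statements about covariates that could bear on this:

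- A general rule: "Analyses of primary and secondary end points will be adjusted for significantly imbalanced baseline characteristics".
- A mediation clause: SAS routines for the potential "confounding influences of time- dependent covariates (e.g. youth age) will be employed as needed in these mediational analyses".

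On the choice of mediators it adds: "In each case, these will include measures that are obtained serially and concurrently with the primary study endpoints". The mediation method is otherwise left to a cited reference.

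The obvious baseline common causes appear in another role: "Candidate moderator variables will include SES, youth age and gender, race/ethnicity, family structure, and health literacy and numeracy". The B.4 schedule collects HbA1c, DSMP-SR, literacy, numeracy and the Knowledge Test at Visit 1, and the General Information Form (B.3) supplies SES and past device use. None is assigned to the mediation models. B.5 names no set of mediator-outcome confounders, states no assumption about unmeasured confounding and plans no sensitivity analysis for it.

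**The concern.** A mediation claim needs two links: SMDM changes decision quality, and decision quality changes device use or satisfaction. Randomization identifies the first. The second is an observational comparison among participants, and anything that drives both variables biases it.

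The protocol makes such common causes plausible. Section A.7 says success with the devices needs suitable cognitive, affective, motivational and environmental resources. The UCP description in B.2 says candidacy typically advances only for patients judged to have enough self-management skill. A numerate, well-organised, already adherent family could score better on Knowledge, SURE and Regret and also use the device more, even if decision quality had no effect.

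Neither provision addresses this. Confounding of the second path operates within each arm and is just as large when the arms are perfectly balanced, so an imbalance test selects on the wrong property. The second provision concerns covariates that change over time, whereas the likely causes are fixed at entry.

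At stake is the trial's explanation of how SMDM works. An association reflecting pre-existing ability could be reported as mechanism. The SMDM-versus-UCP comparisons are not affected.

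**Working it through.** **The plan's own figure.** B.5 gives no error rate or power for mediation. The nearest figure is power of .87 for about 0.4 SD with 150 completers. At 75 per arm and two-sided alpha 0.05 (both from the plan), the noncentrality is 0.4 × √(75/2) = 2.449, and power = Φ(2.449 − 1.96) = 0.69. The .87 is not reproduced. The point does not depend on it; 0.69 serves below as the chance of detecting the SMDM-to-mediator path.

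**Inputs from the plan.** 1:1 allocation; two-sided alpha 0.05; 150 completers; 0.4 SD effect on decision quality.

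**Assumptions.** One baseline common cause C correlates r with both mediator and outcome within arm. The mediator has no effect on the outcome. Mediation is declared when both paths have p < 0.05. About 76 participants have device data, since B.3 takes downloads only from device users.

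**Model.** With unit within-arm variances, M = 0.4T + rC + e₁ and Y = rC + e₂.

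**Step 1: spurious slope.** Cov(M, Y | T) = r², so the slope of Y on M given T is r²: 0.04, 0.09, 0.16 and 0.25 SD per SD at r = .2, .3, .4 and .5.

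**Step 2: chance that it is significant, n = 150.** The test statistic centres on r²√147/√(1 − r⁴) = 0.485, 1.096, 1.965 and 3.130. Against a critical value of 1.976 the chances are 0.075, 0.190, 0.496 and 0.876.

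**Step 3: the imbalance rule.** In a randomized trial C passes a 5% balance test in about 5% of trials, so the rate becomes 0.95 × (step 2) + 0.05 × 0.05 = 0.074, 0.183, 0.473 and 0.835. The rule removes almost nothing.

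**Step 4: both paths.** Multiplying by 0.688 gives 0.05, 0.13, 0.33 and 0.57. Simulations of 4,000 to 10,000 trials per setting agree:

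| r | Imbalance rule, n = 150 | Always adjusted*, n = 150 | Imbalance rule, n = 76 | Always adjusted*, n = 76 |
|---|---|---|---|---|
| .2 | 0.05 | 0.03 | 0.03 | 0.02 |
| .3 | 0.13 | 0.04-0.05 | 0.05 | 0.02-0.03 |
| .4 | 0.33-0.34 | 0.05-0.06 | 0.11 | 0.03 |
| .5 | 0.56-0.59 | 0.08-0.10 | 0.22-0.23 | 0.04 |

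*Using a baseline measure of C with reliability .80, in line with the DSMP-SR internal consistency of .80 to .82 in B.3. With C measured perfectly the rate is about 0.04 at every r (n = 150).

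**Step 5: sensitivity to the first path.** If SMDM shifts the mediator by 0.8 SD (assumed), the n = 150 rates are 8%, 18%, 48% and 83%. If it does not shift the mediator, they are 1% at r = .3 and 4% at r = .5.

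**Step 6: also requiring a significant SMDM effect on the outcome (n = 150; r = .3, .4, .5).** With no SMDM effect on the outcome the rates are at most 0.03. With a direct effect of 0.4 SD they are 0.09, 0.23-0.25 and 0.43-0.44, against 0.03, 0.04 and 0.07-0.08 after adjustment.

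All rates are for one mediator and one outcome. Hypothesis 3 has four mediators and more than one outcome, and parent and youth scores are analysed separately unless they correlate above .70. The chance of at least one false finding is therefore higher.

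**The case against.** The other side has several good points.

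- **The text is not exclusive.** A reader might infer that age is the only covariate allowed, or that common causes must stay unadjusted. The documents do not say so. Age is given as an example, use is as needed, and the imbalance sentence does not forbid other terms. Age at each visit also carries age at entry, so it is not an empty adjustment. What stands is that the confounder set is unspecified and discretionary, and that time-fixed causes have no planned way in except chance imbalance.
- **A reader might infer that false mediation is likely.** The documents do not support that. The rate passes one half only near r = .5 with n = 150 and a real SMDM effect on the mediator; with a 0.8 SD shift, just above r = .4. The device-use subset gives much lower rates. The published adherence figure, "Correlation with HbA_{1c} was .46 for parents and .37 for youths", cannot calibrate r, because neither variable is a Hypothesis 3 mediator or a device-use index.
- **The test is assumed.** Joint significance is not named in the plan. Requiring a total effect lowers the rates, but step 6 shows that inflation remains when SMDM has a direct effect.
- **The hypothesis speaks of change.** For the Knowledge Test, a change score with a stable cause loading equally at both visits brings the rate to 0.02-0.03 (n = 150). Entering baseline as a covariate instead leaves 0.12, 0.27 and 0.50 at r = .3, .4 and .5. Decision Regret and SURE offer no such relief: "The SURE Test will be completed by parents and youth in both groups at Visit 3 and at Visit 5", with no baseline, and Regret has the same schedule.
- **Adjustment is not free or complete.** Parent and youth versions of everything would make a long list, and motivation is not among the measures listed in the schedule. This shapes the fix rather than removing the need for one.

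**Conclusion.** The concern holds in a limited form. As written, the Hypothesis 3 models give time-fixed common causes of decision quality and device outcomes no planned adjustment. The imbalance rule cannot supply it, because it admits such a variable in about 5% of trials whatever its prognostic strength.

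The bias in the mediator-to-outcome slope is about r² in SD units, and the false-mediation rate rises accordingly: from about 5% at r = .2 to 56-59% at r = .5 with 150 participants, and from about 3% to 23% with 76. These figures rest on assumed correlations, an assumed device-user count, a 0.4 SD effect on the mediator, a post-treatment mediator score and a joint-significance test. The direction of the problem does not depend on those exact values; its size does, and the documents do not fix it.

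This should be corrected before the mechanism is analysed. It is not a threat to the randomized comparisons.

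**What to change.** In B.5, add to the mediation text: in the Hypothesis 3 models, both the mediator and the outcome equations will adjust, whatever the baseline balance, for Visit 1 DSMP-SR, HbA1c, health literacy and numeracy, SES and age, plus the Visit 1 Knowledge score where Knowledge is the mediator. For each construct, use one parent or youth score, matched to the respondent analysed. Report the indirect effect with and without these terms, and state that the conclusion assumes no further common causes, naming motivation as one that may remain.

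**Cost.** Wording and model terms only; every variable is already scheduled at Visit 1. Matching scores to the respondent keeps the set to six terms, or seven with Knowledge. Entering both parent and youth versions would need 4 × 2 + 3 = 11, which is heavy for about 76 device users. Some covariates will be missing: B.3 requires the Knowledge, literacy and numeracy tests in person, while Recruitment Plan C enrols families remotely, so the SAP should say how missing covariates are handled. Adjustment reduces the bias without abolishing it, as the 0.08-0.10 left at r = .5 with n = 150 shows.

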Each parent/adolescent dyad will receive a \$25 gift card to a discount retail chain after completing the measurement protocol at Visits 1, 3 and 5, which are the most burdensome of the visits. At each study visit in which an adolescent brings either an insulin pump or CGM to the visit for downloading, the adolescent will receive a \$5 gift card for each such device that is downloaded.

Measures obtained at Baseline only

Demographic characteristics will be measured at study entry using a General Information Form as in our previous studies. This measure ascertains the child's age, diabetes duration, gender, race/ethnicity, and relevant medical history (including past CSII or CGM use) and the parents' income, educational level, occupational category, family structure, race/ethnicity, gender and age. The Hollingshead Four Factor Index of Social Status¹⁵⁹ will be calculated to quantify household socioeconomic status. Participants will be asked to indicate their preferred mode of contact from study staff (e.g. text, phone, e-mail, specific social media). Administration time is about 15 minutes.

Rapid Estimate of Adult/Adolescent Literacy in Medicine This brief test of health literacy will be administered in person to parents and adolescents by the research coordinator at baseline.¹⁶⁰

Diabetes Numeracy Test This 14-item test of numeracy skills pertinent to T1D care will be administered in person to parents and adolescents by the research coordinator at baseline.¹⁶¹

Measures obtained at all 5 quarterly clinic visits

Glycated hemoglobin: Finger-Stick blood samples will be obtained at each quarterly visit and glycated hemoglobin (HbA_{1C}) will be determined using the point of care device currently used at each clinic (typically a DCA2000 or DCA2000plus). These devices have been found to yield results that are highly correlated with benchmark central laboratory assays and that are considered to be acceptable outcomes measures in diabetes clinical trials. HbA_{1C} reflects average glycemia over the prior 2-3 months and is considered a secondary outcome measure in this study.

Hypoglycemia Diary: Parents will record each episode of moderately severe (symptomatic and requiring

assistance from others) or severe hypoglycemia (with seizure or loss of consciousness) using a diary form developed for this purpose in [name] ongoing CGM trial. Frequency of moderately severe and severe hypoglycemia is considered a secondary outcome measure in this study.

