Data Management and Statistical Analysis Plans The primary efficacy endpoints are indices of extent of engagement in CSII (mean number of bolus infusions/day; mean number of uses of "wizard" functions/day) or CGM use (mean number of hours of CGM use/day); and measures of decision quality (Test of CSII or CGM Knowledge; SURE Test; Decision Regret Scale; Diabetes Technology Questionnaire) at each post-decision visit. Secondary efficacy endpoints will include: HbA_{1c} measured quarterly, treatment adherence (DSMP-SR parent and youth) total scores obtained at Visits 1, 3 and 5; and Hypoglycemia Diary obtained at each quarterly clinic visit.

The Full Analysis Set will consist of all participants who provided at least one post baseline assessment record. The Completer Analysis set will include all participants who provided all post baseline primary efficacy assessment results.¹⁶⁶⁻¹¹⁶⁸ Efficacy analyses will be performed on both sets, providing both "Intention to Treat" (Full Analysis Set) and "Per-Protocol" (Completer Analysis Set) analyses. All collected data will be summarized in graphs and tables. Categorical variables will be summarized using frequencies and percentages, while quantitative variables will be described by presenting mean, median, standard deviation (or standard error of mean), minimum and maximum. Data will be summarized by group (SMDM and UCP) and type of medical decision (CSII or CGM) as well as assessment time points. Besides tabular presentation, graphical presentations of some important variables related to primary and secondary endpoints will be provided.

Assumptions for all proposed models will be checked before statistical analyses.¹⁶⁶⁻¹⁶⁸ Appropriate transformations or non-parametric methods will be used in cases of violated model assumptions. For graphical comparison of data that are sufficiently normally distributed, group means and SE of mean will be presented via bar charts. In case of substantial deviation from normality, side by side boxplots will be used for graphical comparisons. Exploratory Subgroup analyses will be conducted as needed. All tests will be performed against a two-sided alternative at the $\alpha = 0.05$ significance level and a 95% confidence interval and/or a p-value will be provided for inferential purposes. Data from all clinics will be pooled for the analyses. All analyses will be performed using the most recent version of the SAS statistical software package.

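### Hypothesis 4 predicts significant moderators at an unadjusted 0.05, with no rule for support and two different lists of moderators and outcomes

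*Combined protocol and SAP*

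**What the plan says.** Section B.5 says that mixed models will be used to test five numbered hypotheses. The fourth reads: "Significant moderators of benefit from SMDM along the measured outcomes will include baseline measures of socioeconomic status, health literacy and numeracy, youth age". It also names family structure. That is five variables, and the outcomes are the measured outcomes in general.

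The analysis text above the hypotheses gives another list: "Candidate moderator variables will include SES, youth age and gender, race/ethnicity, family structure, and health literacy and numeracy". That is seven variables, adding gender and race/ethnicity, and moderation is to be evaluated on the primary outcomes only.

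Two of the variables have two respondents. Section B.3 says of literacy, "This brief test of health literacy will be administered in person to parents and adolescents", and of numeracy, "This 14-item test of numeracy skills pertinent to T1D care will be administered in person to parents and adolescents". B.5 combines parent and youth scores when they correlate above .70. "Otherwise, separate analyses will be completed on parent and adolescent scores".

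On error control there is one rule: "All tests will be performed against a two-sided alternative at the" 0.05 level. B.5 states no adjustment, ordering or global test. Its only exploratory label is on as-needed subgroup analyses and is not tied to Hypothesis 4. The Secondary Analyses paragraph places its own analyses in addition to the hypotheses, so Hypothesis 4 is not among them.

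**The concern.** A treatment-by-moderator interaction is tested for each moderator on each outcome, each at 0.05. The number of tests is not fixed, because the two lists differ in both variables and outcomes. Nor does the plan say whether Hypothesis 4 is supported by one significant interaction, by all five, or by something in between. A reader of the final report could not tell a predicted moderator from one picked out of many tests.

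The result is meant to be used. The budget justification (Other Expenses) says minority enrolment matters scientifically because it permits analyses of whether the intervention works equally well in important subgroups. Yet race/ethnicity is on the candidate list and absent from Hypothesis 4. A chance finding here could lead someone to direct the intervention towards, or away from, particular families.

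**Working it through.** **Plan's own figures.** There is no error rate or power for Hypothesis 4 to reproduce. The only power figure is 0.87 for a main effect of about 0.4 SD with 150 completers. Two-sided 0.05 with 75 per arm gives 0.69, so that figure does not reproduce. That is a separate matter and is not used below.

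**Inputs.**
- Moderators in Hypothesis 4: 5. Candidate list: 7. If parent and youth literacy and numeracy stay separate, each list grows by 2, to 7 and 9.
- Primary endpoints in B.5: boluses/day, wizard uses/day, CGM hours/day, knowledge test, SURE Test, Decision Regret Scale, Diabetes Technology Questionnaire: 7.
- B.3 (device downloads) allows the device scores to be standardised and combined. If the three device indices become one, 7 − 3 + 1 = 5 endpoints remain.
- Alpha 0.05 two-sided per test; 150 completers; 1:1 allocation.
- Correlations among moderators and among endpoints: not in the documents; assumed 0 to 0.8.

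**Chance of at least one nominally significant interaction when none is real.** With independent tests this is 1 − 0.95^k:
- 5 × 1 = 5 tests: 1 − 0.95^5 = 0.23
- 5 × 5 = 25 tests: 1 − 0.95^25 = 0.72
- 5 × 7 = 35 tests: 1 − 0.95^35 = 0.83

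With correlation, z-statistics were simulated with the stated correlation among moderators and among endpoints, counting any |z| > 1.96. For Hypothesis 4's five moderators:

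| Correlation: moderators / endpoints | 7 endpoints | 5 endpoints (device indices merged) |
|---|---|---|
| 0 / 0 | 0.83 | 0.72 |
| 0.3 / 0.3 | 0.77 | 0.66 |
| 0.5 / 0.5 | 0.64 | 0.55 |
| 0.5 / 0.7 | 0.53 | 0.46 |
| 0.7 / 0.7 | 0.45 | 0.39 |
| 0.8 / 0.8 | 0.33 | 0.29 |

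On one endpoint the five tests give 0.23, 0.18 and 0.13 at moderator correlations of 0, 0.5 and 0.8.

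The expected number of false positives does not depend on correlation: 35 × 0.05 = 1.75, or 25 × 0.05 = 1.25.

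Repeated visits, separate parent and youth outcome scores, the two analysis sets and the secondary outcomes would add tests. They are not counted.

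**Power for an interaction, 150 completers, outcome SD 1.**
- Binary moderator split 50/50: SE = 4/√150 = 0.327. For 0.4 SD, 0.4/0.327 = 1.22 and power is about 0.23. An 80% chance needs (1.96 + 0.84) × 0.327 = 0.92 SD.
- Continuous moderator: SE = 2/√150 = 0.163. Power is 0.69 for 0.4 SD per SD of the moderator, or 0.34 if the slope is rescaled to match a 0.4 SD median-split contrast.
- Device endpoints exist only for device users, so power there is lower.

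**The case against.** Four points on the other side have force.

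First, a reader might infer that a false moderator claim is likelier than not. The documents do not support that as a flat statement. They give no correlations, and in the table two of the six settings with seven endpoints, and three of the six with merged device scores, fall below one half.

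Second, a reader might infer that any single p below 0.05 would confirm Hypothesis 4. No such rule is written. Read literally, the hypothesis predicts that all five variables moderate, and one chance result would not confirm that. What stands is that no rule is given, so a single nominal result could be presented as support. Likewise, a significant result for gender or race/ethnicity could not support Hypothesis 4, which names neither; so the calculation uses its own five variables.

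Third, confirmatory is not the plan's word. The analysis text speaks of candidates, the abstract of examining selected variables, and Specific Aim 3 does not mention moderators. This lowers the stakes, but Hypothesis 4 is still a numbered prediction of significance, tested at 0.05 and not labelled exploratory.

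Fourth, a reader might infer that most reported moderators would be chance findings. At power 0.23 and alpha 0.05 that requires fewer than 0.05/(0.05 + 0.23) = 18% of the tested interactions to be real. If half were real, about 0.23/0.28 = 82% of significant results would be genuine. The documents give no basis for choosing.

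**Conclusion.** The point holds as one of labelling, consistency and error control on a numbered hypothesis. The two parts of B.5 disagree on the moderators (five or seven) and on the outcomes, and no criterion for support is stated. Under no true moderation, the chance of at least one nominally significant interaction is several times 0.05 in every setting examined, from 0.13 on one endpoint with highly correlated moderators to 0.83 across seven endpoints with independent tests. The position within that range depends on assumed correlations and on whether the device scores are merged.

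Power for interactions is limited. The figure of 0.23 belongs to an evenly split binary moderator and should not be applied to age, SES, literacy or numeracy kept as scores.

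The main comparison of the two arms is unaffected. The change should be made because it alters what can be concluded from Hypothesis 4 at almost no cost.

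**What to change.** In B.5, use one moderator list and one outcome set, the primary outcomes, in both the analysis text and Hypothesis 4. State whether race/ethnicity and gender are on the list, and how parent and youth literacy and numeracy scores enter. Reword Hypothesis 4 along these lines: moderation of the treatment effect on the primary outcomes by the listed baseline variables will be explored; treatment-by-moderator interaction estimates will be reported with 95% confidence intervals; no moderator will be claimed on an unadjusted p-value.

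If a moderator claim is wanted, apply Holm across the fixed moderator-by-outcome family. For five moderators and seven endpoints the first threshold is 0.05/35 = 0.0014, which the interaction power above makes hard to meet. A global interaction test used as a gate would need a named lead endpoint, which B.5 does not provide.

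The cost is wording only: no new data, visits or participants. The price is that Hypothesis 4 can no longer be declared supported on a nominal p-value.
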